13 DATA SAFETY MONITORING

Adverse events

Definitions and reporting

An adverse event is defined as the appearance of (or worsening of any pre-existing) undesirable sign(s), symptom(s), or medical condition(s) that occur after patient's signed informed consent has been obtained.

Abnormal laboratory values or test results occurring after informed consent constitute adverse events only if they induce clinical signs or symptoms, are considered clinically significant, require therapy (e.g., hematologic abnormality that requires transfusion or hematological stem cell support), or require changes in study medication(s).

Adverse events that begin or worsen after informed consent should be recorded in the Adverse Events CRF. Conditions that were already present at the time of informed consent should be recorded in the Medical History page of the patient's CRF. Adverse event monitoring should be continued for at least 30 days (or 5 half-lives, whichever is longer) following the last dose of study treatment. Adverse events (including lab abnormalities that constitute AEs) should be described using a diagnosis whenever possible, rather than individual underlying signs and symptoms. When a clear diagnosis cannot be identified, each sign or symptom should be reported as a separate Adverse Event.

Adverse events will be assessed according to the Common Terminology Criteria for Adverse Events (CTCAE) version 4.03. If CTCAE grading does not exist for an adverse event, **the severity of mild, moderate, severe, and life-threatening, corresponding to Grades 1 - 4, will be used.**

The occurrence of adverse events should be sought by non-directive questioning of the patient at each visit during the study. Adverse events also may be detected when they are volunteered by the patient during or between visits or through physical examination, laboratory test, or other assessments. As far as possible, each adverse event should be evaluated to determine:

1. The severity grade (CTCAE Grade 1-4)
2. Its duration (Start and end dates or if continuing at the Safety Follow-up Visit)
3. Its relationship to the study treatment (Reasonable possibility that AE is related: No, Yes)
4. Action taken with respect to study or investigational treatment (none, dose adjusted, temporarily interrupted, permanently discontinued, hospitalized, unknown, not applicable)
5. Whether medication or therapy was given (no concomitant medication/non-drug therapy, concomitant medication/non-drug therapy)
6. Outcome (not recovered/not resolved, recovered/resolved, recovering/resolving, recovered/resolved with sequelae, fatal, unknown)
7. Whether it is serious, where a serious adverse event (SAE) is defined as in Section 8.2.1

All adverse events should be treated appropriately. Such treatment may include changes in study drug treatment including possible interruption or discontinuation, starting or stopping concomitant treatments, changes in the frequency or nature of assessments, hospitalization, or any other medically required intervention. Once an adverse event is detected, it should be followed until its resolution, and assessment should be made at each visit (or more frequently, if necessary) of any changes in severity, the suspected relationship to the study drug, the interventions required to treat it, and the outcome.

Information about common side effects already known about the investigational drug can be found in the [Investigators' Brochure \(14\)](#). This information should be included in the patient informed consent and should be discussed with the patient during the study as needed.

Internal Monitoring**13.1 Data Reporting**

Data will be captured in Oncore, Moffitt's Clinical Trials Database.

Regulatory documents and case report forms will be reviewed routinely by the MCC Clinical Research Monitoring Core for accuracy, completeness, and source verification of data entry, validation of appropriate informed consent process, adherence to study procedures, and reporting of SAEs and protocol deviations according to MCC Monitoring Policies.

13.2 Study Suspension/Termination

The Protocol Monitoring Committee (PMC) and/or the IRB may vote to suspend or terminate approval of a research study not being conducted in accordance with the IRB, the Cancer Center and/or regulatory requirements or that has been associated with unexpected problems or serious harm to subjects. The PMC/IRB will notify the PI in writing of such suspension or terminations. It is the responsibility of the PMC/IRB Chairperson to ensure prompt written notification of any suspensions or terminations of PMC/IRB approval to the relevant Federal Agencies, including OHRP, FDA, the study sponsor/funding source and if applicable, the Affiliate Program.

13.3 Trial Discontinuation

For reasonable cause, the Investigator and/or sponsor (Novartis/Moffitt Cancer Center) may terminate this study prematurely. Conditions that may warrant termination include, but are not limited to: the discovery of an unexpected, significant, or unacceptable risk to the patients enrolled in the study or if the accrual goals are met. A written notification of termination will be issued.

14 INCLUSION OF PATIENTS AND MINORITIES:

All patients regardless of ethnicity, race or gender are encouraged to participate in clinical trials. This trial is a treatment for metastatic breast cancer. Based on the fact that only 1% of all breast cancers occur in men, this trial will weighted towards women. Men with breast cancer are encouraged to participate.

15 CORRELATIVES**15.1 Biomarkers in a sub-group of patients**

All patients will have the option to provide a representative tumor specimen upon progression. Our goal is to attain 10 specimens (volunteers). Patients may supply a tumor specimen that may be from a previous biopsy (archival tumor specimen) or a newly obtained tumor specimen. Additionally, a pathology report if available must be submitted along with the patient's archival tumor block/slides.

Genetic aberrations that lead to a gain in CDK signaling are observed in breast cancer. Investigating aberrations of the CDK pathway of patients enrolled in this study will therefore allow for the assessment of the potential predictive value of pathway activation for benefit from ribociclib in metastatic breast cancer. Biomarkers allowing identification of markers of resistance to treatment will also be investigated.

Tumor and blood samples will be collected according to [Table 15-1](#).

All assessments will be performed by a Novartis designated laboratory. Instructions for collection, preparation and shipment can be found in the laboratory manual. Optional sample collection information must be entered on the appropriate eCRF pages and requisition forms.

Tumor samples will be taken pre-treatment and following progression. Tumor tissue samples will be obtained only from patients whose tissue is accessible to minimally invasive biopsy (fine needle aspiration, core needle, or superficial excision biopsy).

The pre-treatment (baseline) biopsy sample may be taken anytime between discontinuation of last endocrine therapy or after cytotoxic therapy and the start of study treatment. If not accessible, an archival sample from metastatic site is allowed. A pathology report must be submitted along with the patient's archival tumor block/slides.

Biopsy collection is requested (optional) at time of tumor progression for identifying potential markers of lack of response/resistance.

Tumor samples will be tested retrospectively for Rb protein and PTEN protein by immunohistochemistry. The status of molecules (e.g., gene expression, mutations, amplifications, deletions and/or protein expression/activation etc.) that are involved in the D-cyclin-CDK4/6-INK4a-Rb and mTOR pathways, such as mutations of CCND1, PIK3CA, PTEN and CDK4; gene amplification of CCND1 and CDK4, deletion of CDKN2, as well as potential resistant/escape pathways to CDK 4/6 inhibitors and other cancer associated genes, will also be investigated in the tumor tissue from all patients (provided that acceptable assays exist), with the intention of understanding potential mechanisms of resistance to CDK 4/6 inhibitors and identify the patient population that would benefit from this combination.

The results from these exploratory analyses will be correlated with clinical outcome to determine potential predictive biomarkers of ribociclib/everolimus/exemestane response.

Table 15-1 Biomarker sample collection plan

Sample	Tissue/Volume	Visit	Sample Collection
Baseline tumor biopsy for predictive markers (optional) if accessible, if not accessible based on surgical evaluation, then archival tissue from metastatic site allowed)	N/A	Screening	Following progression on prior treatment and prior to Cycle 1 Day 1

Newly obtained post-progression tumor samples for resistance (optional)	N/A	Post- progression	At progression and before new treatment is initiated
Exploratory Circulating tumor DNA (mandatory)	Blood/Plasma 20mL	Screening or Cycle 1, day 1	Predose
	Blood Plasma 10mL	Cycle 3 Day 1 Cycle 5 Day 1 Cycle 7 Day 1	Predose
	Blood/plasma 20ML	End of treatment	Within 15 days from last dose

Biomarkers assessment for pathway inhibition and efficacy

Assessments in tumor tissue

Tumor tissue samples will be collected in this trial for identifying biomarkers that may be predictive of benefit from ribociclib + Tamoxifen. Approximately 15-20 unstained slides (minimum of 10) should be made available for biomarker studies. If a biopsy is not possible, then an archival Formalin-Fixed, Paraffin-Embedded (FFPE) tumor will be acceptable (metastatic lesion preferred).

All specimens will be sent to a Novartis designated laboratory for analysis. Further details on preparation of the tumor biopsies and biomarker analysis will be provided in the Laboratory Manual.

Exploratory circulating tumor DNA

Assessment of circulating tumor DNA (ctDNA) will allow additional testing for mutations of genes that are relevant to HR+ breast cancer (e.g. PIK3CA, AKT, ESR1) and the CDK4/6 pathway using multiplexed approach such as next generation sequencing. The use of ctDNA offers a unique opportunity for serially monitoring tumor mutations in a non-invasive manner during the course of treatment, allowing for the detection of changes in tumor burden and monitoring response to treatment ([Esposito et al 2014](#)). Evaluation of tumor mutations at time of progression may provide information regarding potential mechanisms of resistance to therapy with ribociclib + tamoxifen. Blood samples for plasma ctDNA will be collected at baseline (20 mL at screening or cycle 1 day 1) and then day 1 of cycles 3, 5, 7 and end of treatment (20mL) for multiplexed analysis of cancer genes.

Exploratory analysis of potential mechanism of resistance

The biopsy collected at progression/end of treatment will be dedicated to understanding resistance to treatment. This study provides a unique opportunity to investigate the potential mechanisms of resistance to ribociclib in patients.

The specimens will be handled and shipped as described in the Laboratory Manual. The sample collection date must be entered on the appropriate tumor biopsy collection log eCRF page(s) and laboratory requisition form(s).

Additional biomarker assessments

During the study, in addition to the biomarkers specified above, exploratory research may be conducted on any tumor and blood samples collected. These studies would extend the search for other potential biomarkers relevant to the effects of ribociclib, goserilin, and Tamoxifen and/or prediction of these effects and/or resistance to the treatment, and/or safety. This may include the development of ways to detect, monitor or treat cancer. These additional investigations would be dependent upon clinical outcome, reagent and sample availability.

While the goal of the biomarkers is to provide supportive data, this is strictly optional in this study.

[REDACTED]

[REDACTED]

[REDACTED]

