- B) Premenopausal patients who have de-novo metastatic disease (metastatic disease at presentation).
- C) Premenopausal women who have not received Tamoxifen in the metastatic setting, but have received up to two lines of chemotherapy.

Post-Menopausal Women or Men

- D) Postmenopausal patients who have progressed on first-line or second-line therapy with an aromatase inhibitor in the metastatic setting
- E) Postmenopausal patients who have recurred while on or after completion of adjuvant treatment with aromatase inhibitors (they have completed at least one year of adjuvant AI in the adjuvant setting before progression on AI).
- F) Postmenopausal patients who are not considered candidates for treatment with an aromatase inhibitor by their oncologist , patients not willing not to go on to AI, or were intolerant to AI
- G) Post-menopausal women or men who have been treated with up to three lines in the escalation arm and up to two lines of chemotherapy in the dose expansion arm in the metastatic setting.

Type of Study

Open labeled, non-randomized; phase I dose escalation followed by phase Ib dose expansion

Prior Therapy

- Progression on any aromatase inhibitor for metastatic disease
- Recurrence ≥ 12 months after commencement of adjuvant aromatase inhibitors
- Patients are allowed (but not required) to have up to two prior chemotherapy regimens for metastatic disease

Rationale for Study

Cell cycle progression is directly regulated by cyclin-dependent serine-threonine protein kinases. The cyclin D proteins are important in cancer, as their abundance and functions are regulated by extracellular growth factor and adhesion signaling. The cyclin D proteins act through the CDK4 and CDK6 protein kinases to promote G1 progression (1). CDK4 and CDK6, in turn, hyperphosphorylate and activate the retinoblastoma protein Rb to promote cell cycle entry and cell proliferation. Consistent with their having an important role in human cancer, focal copy number abnormalities that result in increased CDK activity are among the most commonly described genetic events observed in diverse tumor types; these events

include amplifications of the genes that encode cyclin D1 or CDK4, and deletions affecting the CDKN2A locus, which encodes the p16INK4a inhibitor of CDK activity (2-4).

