1.4 Role of the CDK4/6 pathway in breast cancer

Cell cycle progression is directly regulated by cyclin-dependent serine-threonine protein kinases (CDKs). Extracellular growth and adhesion signals increase the level and function of cyclin D proteins within the cell. In turn, the cyclin D proteins associate with and activate CDK4 and CDK6 (1). CDK4 and CDK6 phosphorylation leads to inactivation of the retinoblastoma protein (pRb) and thus releases E2F which in turn leads to the transcription initiation of proteins involved in cell cycle propagation and cell proliferation. The luminal A and B subtypes of breast cancer (85% of which are ER+/HER2-negative) have high rates of cyclin D/CDK activation; in the luminal A and B subtypes, cyclin D1 (CCND1) amplifications were observed in 29% and 58%, and CDK4 amplifications were observed in 14% and 25% respectively (5, 9).

Luminal A subtype tumors also have loss of CDKN2A, which encodes p16Ink4a, a CDK inhibitor (12). The luminal subtypes also maintain expression of Rb, which is essential for benefit from treatment with a CDK4/6 inhibitor (4). Dysregulation of cell cycle checkpoints is common in cancer. Modulating the cell cycle has always been an attractive therapeutic target in cancer, and previously published data have suggested that CDK4/6 inhibition may play a key role in the treatment of subsets of breast cancers. Patients with HR+ breast cancer exhibiting a gene expression signature of Rb loss had shorter recurrence-free survival following adjuvant tamoxifen (13). A tumor gene expression signature of E2F activation was associated with higher residual tumor cell proliferation following pre-surgical AI therapy. Therefore, activation of the CDK4/CDK6/E2F axis promotes endocrine resistance, and treatment with a CDK4/6 inhibitor or knockdown of CDK4 expression abrogates endocrine-resistant cell proliferation. In conclusion, loss of cell cycle control is a hallmark of cancer, and aberrations in the cyclin/CDK/Rb pathway are common in breast cancer. Consequently, inhibition of this pathway (at the level of CDK4/6)

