10.2 Statistical Considerations for Phase Ib Dose expansion Study

If no MTD is observed with Level 1 through 3, we plan to continue/conduct the phase Ib dose expansion study as below. This expansion study is planned to understand and obtain initial efficacy data for the secondary endpoints.

Since the identical patient inclusion/exclusion criteria will be used in phase Ib dose expansion, all patient data from phase I dose escalation and phase Ib dose expansion studies can be combined for our statistical analysis, therefore, the required sample size of patients below will be both for phase I dose escalation and phase Ib dose expansion studies.

We obtained our statistical power and required sample size as a single-arm prospective study. In particular, for our evaluation of early efficacy we designed the study particular, for our evaluation of early efficacy we designed the study for testing $H_0: P \leq 0.10$ versus $H_1: P \geq 0.25$ at one-sided significance level 0.05 and power 0.80 as below.

P0	P1	Alpha	Beta	Cut-Off		Actual	Actual
				R + 1	N		
0.100	0.250	0.050	0.200	8	40	0.042	0.182

Where P0 is the maximum response proportion of standard care (tamoxifen alone), P1 is the minimum response proportion of our experimental treatment group, and N is the sample size.

For our statistical testing, if the number of responses $\geq R+1$, P0 is rejected based on Fisher's Exact test (34, 35). Alpha is the probability of rejecting that $P \leq P_0$ when this is true.

Beta is the probability of rejecting that $P \geq P_1$ when this is true.

Thus, the study requires 6 subjects under phase I dose escalation and 30 subjects under phase Ib dose expansion who will be treated with ribociclib (total 36) in order to test whether the proportion responding, P, is less than or equal to 0.100 or greater than or equal to 0.25. If the number of responses is 8 or more, the hypothesis that $P \leq 0.100$ is rejected with a target Type I error rate, α , of 0.050 and an actual error rate of 0.045. The null hypothesis will be rejected if 8 or more responses are observed in 40 patients. This design yields a type I error rate of 0.045 and power of 0.818 when the true response rate is 0.25.

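### Section 15.1 says marker-outcome correlation in this single-arm trial will allow assessment of predictive value for ribociclib benefit, but the design cannot separate prognostic from predictive effects

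*Combined protocol and SAP*

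**What the plan says.** The synopsis gives the type of study as "Open labeled, non-randomized; phase I dose escalation followed by phase Ib dose expansion". Section 10.2 adds: "We obtained our statistical power and required sample size as a single-arm prospective study". All five cohorts in Table 8-1 receive ribociclib and tamoxifen; they differ only in ribociclib dose and schedule.

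Section 15.1 states that investigating CDK-pathway aberrations "will therefore allow for the assessment of the potential predictive value of pathway activation for benefit from ribociclib in metastatic breast cancer". It also intends to "identify the patient population that would benefit from this combination". The method is a single sentence: "The results from these exploratory analyses will be correlated with clinical outcome to determine potential predictive biomarkers of ribociclib/everolimus/exemestane response". The paragraph on assessments in tumor tissue repeats the aim of finding markers predictive of benefit, this time from ribociclib plus tamoxifen. No test, effect measure or null hypothesis is given, and clinical outcome is not defined there.

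Rb and PTEN protein are to be tested by immunohistochemistry on tumor tissue. Tissue is optional, with a goal of 10 specimens. Table 15-1 lists circulating tumor DNA as mandatory.

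Section 1.4 gives two statements about Rb. One is: "Patients with HR+ breast cancer exhibiting a gene expression signature of Rb loss had shorter recurrence-free survival following adjuvant tamoxifen". The other, in the same paragraph, is that Rb expression is essential for benefit from a CDK4/6 inhibitor.

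**The concern.** A marker is predictive for ribociclib if the ribociclib effect differs by marker status. To see that, one needs outcomes with and without ribociclib in each marker group, and this trial collects only the first. The only external comparator in the plan is one overall tamoxifen response rate of about 10%, not split by marker. The dose and schedule cohorts are neither randomised nor ribociclib-free, so they cannot serve as controls.

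The natural reading of correlating markers with clinical outcome is a test of no association with outcome on the combination. A marker that changes prognosis alone would make that hypothesis false while the ribociclib effect is identical in both marker groups. Section 15.1 says the data will allow the predictive question to be assessed, which is a property the design lacks. At stake is how marker results are labelled in the report.

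**Working it through.** **The plan's own figures.** None is given for the marker analysis. The one powered analysis is the response rule in Section 10.2 (8 or more responses in 40, 10% against 25%). Exact binomial tails give 0.0419 and 0.8180, matching the table's alpha of 0.042 and the stated power of 0.818. The 0.045 in the text does not reproduce, which is a separate matter. This rule says nothing about markers.

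**What can be identified.** Let the prognostic ratio be the marker-positive to marker-negative hazard ratio on tamoxifen alone, and the predictive ratio be the ribociclib hazard ratio in marker-positive patients divided by that in marker-negative patients. Then:

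observed hazard ratio on the combination = prognostic ratio × predictive ratio.

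An observed ratio of 2 fits 2 × 1 (prognostic only), 1 × 2 (predictive only) or 4 × 0.5 (prognostic, with more ribociclib benefit in marker-positive patients). There is one observed quantity and two unknowns. More patients in the same arm only estimate the product more precisely.

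**Illustration of size.** The documents give no marker prevalence or prognostic effect, so these inputs are assumed: predictive ratio 1; prognostic hazard ratio 2; prevalence 30% or 50%; tamoxifen median time to progression 6 months; ribociclib hazard ratio 0.6 in both marker groups; 24 months of follow-up; two-sided 5% log-rank test. N = 40 is the planned total and N = 10 the tissue goal.

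A closed-form check with all patients having events uses d = √(N·q·(1−q)) × ln 2 and rejection probability Φ(d − 1.96) + Φ(−d − 1.96):

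| N | prevalence q | d | formula | simulated log-rank |
|---|---|---|---|---|
| 40 | 0.3 | √8.4 × 0.693 = 2.009 | 52% | 48-50% |
| 40 | 0.5 | √10 × 0.693 = 2.192 | 59% | 52-54% |
| 10 | 0.3 | √2.1 × 0.693 = 1.004 | 17% | about 19% |
| 10 | 0.5 | √2.5 × 0.693 = 1.096 | 19% | 17-19% |

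With no marker effect at all, the simulated test rejects about 5% at N = 40 and about 7% at N = 10. Part of the excess at N = 10 is therefore small-sample error of the test.

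**What a control would change.** In a separate simulation (exponential times without censoring, Wald tests, 30% prevalence, prognostic hazard ratio 2), the single-arm test rejects 22%, 54% and 99.6% at n = 10, 40 and 200. A marker-by-treatment interaction test, with a tamoxifen-alone arm of equal size added, rejects 7%, 5% and 5%. Single-arm rejection rises with sample size, so a larger trial of this type is no remedy.

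**Response endpoint.** Two-sided Fisher test, half of patients marker-positive, 10% against 40% response (assumed): exact enumeration gives 0.055 at N = 10 (5 and 5) and 0.49 at N = 40 (20 and 20). At N = 10 the test is conservative and has little chance of flagging anything.

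**The case against.** **The text is hedged.** Section 15.1 calls the work exploratory, speaks of potential predictive markers, describes the data as supportive and ends by calling the work strictly optional. Section 3 has no predictive-marker objective, and no decision depends on the results. This stands, and it lowers the severity. It does not supply the missing comparison: hedging says the evidence is weak, whereas the design cannot provide this kind of evidence at any strength.

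**Much of the wording concerns the combination.** Markers of outcome on ribociclib plus tamoxifen can be described in one arm. That is fair, and it is what the fix keeps. The sentence on benefit from ribociclib goes further, and so does identifying who would benefit.

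**The illustration rests on assumptions.** True. In addition, N = 40 applies to circulating tumor DNA, not to Rb, which is tested on optional tissue. Section 1.4 says luminal tumors maintain Rb, so Rb loss may be rarer than 30%. At N = 10 with an assumed 5-10% prevalence, rejection at a hazard ratio of 2 is only 7.5-13%. With so few specimens the problem is interpretation more than a count of false positives.

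**Some text is unseen.** Part of Section 15 is redacted and assay detail is left to the Laboratory Manual, so a caveat there cannot be ruled out. The visible claims need correcting regardless.

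**Stronger readings to avoid.** A reader might infer that the protocol reports Rb loss as prognostic only, so that the same difference is expected on tamoxifen alone. It does not: Section 1.4 also gives Rb a predictive role, and the tamoxifen finding is a gene-expression signature in the adjuvant setting, whereas the trial tests Rb protein in advanced disease. A reader might also infer that false rejection is at least double the nominal rate in every setting. The Fisher result at N = 10 and the 7% log-rank baseline there contradict that.

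**Conclusion.** The point holds as one about interpretation. Section 15.1 credits the design with an ability to assess predictive value that it does not have, and a purely prognostic marker could be labelled potentially predictive. That conclusion follows from the absence of tamoxifen-alone outcomes by marker status and needs no numerical assumption. The rejection rates (about half at N = 40 and 17-19% at N = 10 for log-rank) depend on the assumed hazard ratio and prevalence and only illustrate scale. Rb is a fair example of a marker whose two roles, both mentioned in Section 1.4, cannot be told apart here. Severity is low: no endpoint, sample size or primary inference is affected, and the documents do not show that a later trial's patient selection would rest on these results.

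The regimen named in the method sentence includes everolimus and exemestane, which are not study treatments in this trial. That is a separate text error.

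**What to change.** Reword Section 15.1, including the paragraph on assessments in tumor tissue, along these lines:

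*Marker status will be described by its association with response and time to progression on ribociclib + tamoxifen, with estimates and confidence intervals. Because there is no tamoxifen-alone group, these associations do not separate prognostic from predictive effects. They are hypothesis-generating and will not be reported as predictive of ribociclib benefit.*

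Remove the aim of identifying the population that would benefit as something this trial can conclude. Correct the regimen in the method sentence to ribociclib + tamoxifen. Do not add a statement that an Rb or E2F association is expected on endocrine therapy alone; the documents do not establish that.

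The cost is wording only, with no extra patients, samples or assays. The downside is losing a stronger-sounding exploratory claim. Adding a small control arm would not be a proportionate alternative. To detect a ratio of hazard ratios of 0.5 with 80% power at two-sided 5%, 1:1 allocation and 50% prevalence (all assumed) takes (1.96 + 0.842)² / (0.25 × 0.25 × (ln 0.5)²), or about 262 events, far beyond a 40-patient trial.
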